# Responder for HbA1c after 26 weeks of treatment

Two dichotomous endpoints (responder/non-responder) will be defined based on whether a subject has met a specific target level after 26 weeks of treatment:

- ADA HbA1c target (HbA1c < 7.0%)
- International Diabetes Federation (IDF)  $HbA_{1c}$  target ( $HbA_{1c} \le 6.5\%$ )

Analysis of each of the two responder endpoints will be based on a logistic regression model with treatment and previous anti-diabetic treatment as fixed factors and baseline HbA1c value as a covariate.

### HbA1c responder endpoints without weight gain

Responder for  $HbA_{1c}$  without weight gain after 26 weeks of treatment will be defined as  $HbA_{1c} < 7.0\%$  or  $\le 6.5\%$  at end of treatment and change from baseline in body weight below or equal to zero. Analysis of each of the two responder endpoints will be based on a logistic regression model with treatment and previous anti-diabetic treatment as fixed factors and baseline  $HbA_{1c}$  and body weight values as covariates.

# HbA1c responder endpoints without hypoglycaemic episodes

Responder for  $HbA_{1c}$  without hypoglycaemic episodes after 26 weeks of treatment will be defined as  $HbA_{1c} < 7.0\%$  or  $\le 6.5\%$  at end of treatment and without severe or BG confirmed episodes during the last 12 weeks of treatment. Analysis of each of the two responder endpoints will be based

Protocol Trial ID: NN9068-4148 UTN: U1111-1154-6671	CONFIDENTIAL	Date: Version: Status:	07 October 2014 2.0 Final	Novo Nordisk
		Page:	65 of 84	

on a logistic regression model with treatment and previous anti-diabetic treatment as fixed factors and baseline  $HbA_{1c}$  values as a covariate.

# HbA1c responder endpoints without hypoglycaemic episodes and weight gain

Responder for  $HbA_{1c}$  without hypoglycaemic episodes and weight gain after 26 weeks of treatment will be defined as  $HbA_{1c} < 7.0\%$  or  $\le 6.5\%$  at end of treatment, without severe or BG confirmed episodes during the last 12 weeks of treatment, and change from baseline in body weight below or equal to zero. Analysis of each of the two responder endpoints will be based on a logistic regression model with treatment and previous anti-diabetic treatment as fixed factors and baseline  $HbA_{1c}$  and body weight values as covariates.

### Fasting plasma glucose (FPG)

Change from baseline in FPG after 26 weeks of treatment will be analysed using the standard ANCOVA model.

### Waist circumference

Change from baseline in waist circumference after 26 weeks of treatment will be analysed using the standard ANCOVA model.

### Beta-cell function (fasting insulin, fasting C-peptide, fasting glucagon, and HOMA-β)

In addition to fasting insulin, fasting C-peptide, and fasting glucagon, one derived parameter will be calculated; beta-cell function (HOMA-β).

The calculation of the HOMA endpoint will be done as follows:

• Beta-cell function (%) =  $20 \cdot \text{fasting insulin} [\mu \text{U/mL}]/(\text{FPG}[\text{mmol/L}]-3.5)$ 

These endpoints after 26 weeks of treatment will be analysed separately using the standard ANCOVA model. In these statistical analyses the endpoint will be log-transformed and so will the baseline covariate.

### Fasting lipid profile

Cholesterol, LDL cholesterol, HDL cholesterol, VLDL cholesterol, triglycerides, and free fatty acids after 26 weeks of treatment will be analysed separately using the standard ANCOVA model. In these statistical analyses the endpoint will be log-transformed and so will the baseline covariate.

| Protocol | Trial ID: NN9068-4148 | UTN: U1111-1154-6671 | CONFIDENTIAL | CONFIDENTIAL | CONFIDENTIAL | CONFIDENTIAL | CONFIDENTIAL | CONFIDENTIAL | CONFIDENTIAL | CONFIDENTIAL | CONFIDENTIAL | CONFIDENTIAL | CONFIDENTIAL | CONFIDENTIAL | CONFIDENTIAL | CONFIDENTIAL | CONFIDENTIAL | CONFIDENTIAL | CONFIDENTIAL | CONFIDENTIAL | CONFIDENTIAL | CONFIDENTIAL | CONFIDENTIAL | CONFIDENTIAL | CONFIDENTIAL | CONFIDENTIAL | CONFIDENTIAL | CONFIDENTIAL | CONFIDENTIAL | CONFIDENTIAL | CONFIDENTIAL | CONFIDENTIAL | CONFIDENTIAL | CONFIDENTIAL | CONFIDENTIAL | CONFIDENTIAL | CONFIDENTIAL | CONFIDENTIAL | CONFIDENTIAL | CONFIDENTIAL | CONFIDENTIAL | CONFIDENTIAL | CONFIDENTIAL | CONFIDENTIAL | CONFIDENTIAL | CONFIDENTIAL | CONFIDENTIAL | CONFIDENTIAL | CONFIDENTIAL | CONFIDENTIAL | CONFIDENTIAL | CONFIDENTIAL | CONFIDENTIAL | CONFIDENTIAL | CONFIDENTIAL | CONFIDENTIAL | CONFIDENTIAL | CONFIDENTIAL | CONFIDENTIAL | CONFIDENTIAL | CONFIDENTIAL | CONFIDENTIAL | CONFIDENTIAL | CONFIDENTIAL | CONFIDENTIAL | CONFIDENTIAL | CONFIDENTIAL | CONFIDENTIAL | CONFIDENTIAL | CONFIDENTIAL | CONFIDENTIAL | CONFIDENTIAL | CONFIDENTIAL | CONFIDENTIAL | CONFIDENTIAL | CONFIDENTIAL | CONFIDENTIAL | CONFIDENTIAL | CONFIDENTIAL | CONFIDENTIAL | CONFIDENTIAL | CONFIDENTIAL | CONFIDENTIAL | CONFIDENTIAL | CONFIDENTIAL | CONFIDENTIAL | CONFIDENTIAL | CONFIDENTIAL | CONFIDENTIAL | CONFIDENTIAL | CONFIDENTIAL | CONFIDENTIAL | CONFIDENTIAL | CONFIDENTIAL | CONFIDENTIAL | CONFIDENTIAL | CONFIDENTIAL | CONFIDENTIAL | CONFIDENTIAL | CONFIDENTIAL | CONFIDENTIAL | CONFIDENTIAL | CONFIDENTIAL | CONFIDENTIAL | CONFIDENTIAL | CONFIDENTIAL | CONFIDENTIAL | CONFIDENTIAL | CONFIDENTIAL | CONFIDENTIAL | CONFIDENTIAL | CONFIDENTIAL | CONFIDENTIAL | CONFIDENTIAL | CONFIDENTIAL | CONFIDENTIAL | CONFIDENTIAL | CONFIDENTIAL | CONFIDENTIAL | CONFIDENTIAL | CONFIDENTIAL | CONFIDENTIAL | CONFIDENTIAL | CONFIDENTIAL | CONFIDENTIAL | CONFIDENTIAL | CONFIDENTIAL | CONFIDENTIAL | CONFIDENTIAL | CONFIDENTIAL | CONFIDENTIAL | CONFIDENTIAL | CONFIDENTIAL | CONFIDENTIAL | CONFID

### Self-measured plasma glucose 9-point profile

Three endpoints from the 9-point profile will be defined:

- 9-point profile
- Mean of the 9-point profile, defined as the area under the profile (calculated using the trapezoidal method) divided by the measurement time
- Post-prandial plasma glucose increments (from before meal to 90 min after for breakfast, lunch and dinner). The mean increment over all meals will be derived as the mean of all available meal increments

A mixed effect model will be fitted to the 9-point profile data. The model will include treatment, time, interaction between treatment and time, and previous anti-diabetic treatment as fixed factors and the baseline value as a covariate. An unstructured residual covariance matrix within the same subject is employed. From the model mean profile by treatment and relevant treatment differences will be estimated and explored.

Change from baseline after 26 weeks of treatment in mean of the 9-point profile and post-prandial increment endpoints will be analysed separately using the standard ANCOVA model.

# 17.4.2.2 Safety endpoints

### **Adverse events**

AEs will be coded using the most recent version of the Medical Dictionary for Regulatory Activities coding.

A TEAE is defined as an event that has onset date on or after the first day of exposure to randomised treatment and no later than seven days after the last day of randomised treatment. If the event has onset date before the first day of exposure on randomised treatment and increases in severity during the treatment period and until 7 days after the last drug date, then this event should also be considered as a TEAE.

TEAEs are summarised descriptively, whereas non-TEAEs are presented in listings. TEAE data will be displayed in terms of the number of subjects with at least one event (N), the percentage of subjects with at least one event (%), the number of events (E) and the event rate per 100 years of exposure (R).

Summaries of TEAEs and of serious TEAEs will be presented as an overview including all AEs, serious AEs, number of deaths, AEs by severity, AEs by relation to treatment and AEs of special interest including AEs leading to withdrawal.

Protocol		Date:	07 October 2014	Novo Nordisk
Trial ID: NN9068-4148	CONFIDENTIAL	Version:	2.0	
UTN: U1111-1154-6671	CONFIDENTIAL	Status:	Final	
		Page:	67 of 84	

Furthermore summary tables based on system organ class and preferred terms are made for:

- All TEAEs
- Serious TEAEs
- Possibly or probably related TEAEs
- Severe, moderate and mild TEAEs
- TEAEs reported by safety areas of interest
- TEAEs with preferred term that are experienced by at least 5% of the subjects in any treatment arm or by at least 5% of all subjects

A listing for non-TEAEs with onset date before the first day of exposure to randomised treatment will be presented. A listing will also be presented for non-TEAEs collected after the treatment emergent period according to the definition of TEAE.

# Classification of Hypoglycaemia

**Treatment emergent:** hypoglycaemic episodes will be defined as treatment emergent if the onset of the episode occurs on or after the first day of trial product administration, and no later than 7 days after the last day on trial product.

**Nocturnal hypoglycaemic episodes:** are episodes with time of onset between 00:01 and 05.59 both inclusive.

Hypoglycaemic episodes are classified according to the Novo Nordisk classification of hypoglycaemia (see Figure 17–1) and the ADA classification of hypoglycaemia (see Figure 17–2).

### Novo Nordisk classification of hypoglycaemia

[figure not shown]
In normal physiology, symptoms of hypoglycaemia occur below a plasma glucose level of 3.1 mmol/ $L^{16}$ . Therefore, Novo Nordisk has included hypoglycaemia with plasma glucose levels below this cut-off point in the definition of BG confirmed hypoglycaemia.

Novo Nordisk uses the following classification (in addition to the ADA classification):

• Severe or BG confirmed symptomatic hypoglycaemia: An episode that is severe according to the ADA classification or BG confirmed by a plasma glucose value <3.1 mmol/L with symptoms consistent with hypoglycaemia

Protocol Trial ID: NN9068-4148 UTN: U1111-1154-6671	CONFIDENTIAL	Date: Version: Status: Page:	07 October 2014 2.0 Final 68 of 84	Novo Nordisk
---	--------------	---------------------------------------	---	--------------

• Severe or BG confirmed hypoglycaemia: An episode that is severe according to the ADA classification or BG confirmed by a plasma glucose value <3.1 mmol/L with or without symptoms consistent with hypoglycaemia

[figure not shown]

Note: Glucose measurements are performed with capillary blood calibrated to plasma equivalent glucose values

Figure 17-1 Novo Nordisk classification of hypoglycaemia

# ADA classification of hypoglycaemia 11

- Severe hypoglycaemia: An episode requiring assistance of another person to actively administer carbohydrate, glucagon, or take other corrective actions. Plasma glucose concentrations may not be available during an event, but neurological recovery following the return of plasma glucose to normal is considered sufficient evidence that the event was induced by a low plasma glucose concentration
- Asymptomatic hypoglycaemia: An episode not accompanied by typical symptoms of hypoglycaemia, but with a measured plasma glucose concentration ≤ 3.9 mmol/L
- Documented symptomatic hypoglycaemia: An episode during which typical symptoms of hypoglycaemia are accompanied by a measured plasma glucose concentration ≤ 3.9 mmol/L
- Pseudo-hypoglycaemia: An episode during which the person with diabetes reports any of the typical symptoms of hypoglycaemia with a measured plasma glucose concentration > 3.9 mmol/L but approaching that level
- Probable symptomatic hypoglycaemia: An episode during which symptoms of hypoglycaemia are not accompanied by a plasma glucose determination but that was presumably caused by a plasma glucose concentration ≤ 3.9 mmol/L

Note: Glucose measurements are performed with capillary blood calibrated to plasma equivalent glucose values

# Figure 17–2 ADA classification of hypoglycaemia

Data on treatment emergent hypoglycaemic episodes are presented in terms of the number of subjects with at least one event (N), the percentage of subjects with at least one event (%), the number of events (E) and the event rate per 100 years (R).

Separate summaries are made for severe or BG confirmed hypoglycaemic episodes, severe or BG confirmed symptomatic hypoglycaemic episodes, nocturnal severe or BG confirmed hypoglycaemic episodes, nocturnal severe or BG confirmed symptomatic hypoglycaemic episodes and the ADA classification of hypoglycaemia.

All endpoints based on hypoglycaemic episodes will be analysed using the same model as used for the treatment emergent severe or BG confirmed hypoglycaemic episodes.

#### **Pulse**

Change from baseline in pulse after 26 weeks of treatment will be analysed using the standard ANCOVA model.

### Systolic and diastolic blood pressure

Change from baseline in systolic and diastolic blood pressure after 26 weeks of treatment will be analysed using the standard ANCOVA model.

| Protocol | Trial ID: NN9068-4148 | CONFIDENTIAL | CONFIDENTIAL | CONFIDENTIAL | CONFIDENTIAL | CONFIDENTIAL | CONFIDENTIAL | CONFIDENTIAL | CONFIDENTIAL | CONFIDENTIAL | CONFIDENTIAL | CONFIDENTIAL | CONFIDENTIAL | CONFIDENTIAL | CONFIDENTIAL | CONFIDENTIAL | CONFIDENTIAL | CONFIDENTIAL | CONFIDENTIAL | CONFIDENTIAL | CONFIDENTIAL | CONFIDENTIAL | CONFIDENTIAL | CONFIDENTIAL | CONFIDENTIAL | CONFIDENTIAL | CONFIDENTIAL | CONFIDENTIAL | CONFIDENTIAL | CONFIDENTIAL | CONFIDENTIAL | CONFIDENTIAL | CONFIDENTIAL | CONFIDENTIAL | CONFIDENTIAL | CONFIDENTIAL | CONFIDENTIAL | CONFIDENTIAL | CONFIDENTIAL | CONFIDENTIAL | CONFIDENTIAL | CONFIDENTIAL | CONFIDENTIAL | CONFIDENTIAL | CONFIDENTIAL | CONFIDENTIAL | CONFIDENTIAL | CONFIDENTIAL | CONFIDENTIAL | CONFIDENTIAL | CONFIDENTIAL | CONFIDENTIAL | CONFIDENTIAL | CONFIDENTIAL | CONFIDENTIAL | CONFIDENTIAL | CONFIDENTIAL | CONFIDENTIAL | CONFIDENTIAL | CONFIDENTIAL | CONFIDENTIAL | CONFIDENTIAL | CONFIDENTIAL | CONFIDENTIAL | CONFIDENTIAL | CONFIDENTIAL | CONFIDENTIAL | CONFIDENTIAL | CONFIDENTIAL | CONFIDENTIAL | CONFIDENTIAL | CONFIDENTIAL | CONFIDENTIAL | CONFIDENTIAL | CONFIDENTIAL | CONFIDENTIAL | CONFIDENTIAL | CONFIDENTIAL | CONFIDENTIAL | CONFIDENTIAL | CONFIDENTIAL | CONFIDENTIAL | CONFIDENTIAL | CONFIDENTIAL | CONFIDENTIAL | CONFIDENTIAL | CONFIDENTIAL | CONFIDENTIAL | CONFIDENTIAL | CONFIDENTIAL | CONFIDENTIAL | CONFIDENTIAL | CONFIDENTIAL | CONFIDENTIAL | CONFIDENTIAL | CONFIDENTIAL | CONFIDENTIAL | CONFIDENTIAL | CONFIDENTIAL | CONFIDENTIAL | CONFIDENTIAL | CONFIDENTIAL | CONFIDENTIAL | CONFIDENTIAL | CONFIDENTIAL | CONFIDENTIAL | CONFIDENTIAL | CONFIDENTIAL | CONFIDENTIAL | CONFIDENTIAL | CONFIDENTIAL | CONFIDENTIAL | CONFIDENTIAL | CONFIDENTIAL | CONFIDENTIAL | CONFIDENTIAL | CONFIDENTIAL | CONFIDENTIAL | CONFIDENTIAL | CONFIDENTIAL | CONFIDENTIAL | CONFIDENTIAL | CONFIDENTIAL | CONFIDENTIAL | CONFIDENTIAL | CONFIDENTIAL | CONFIDENTIAL | CONFIDENTIAL | CONFIDENTIAL | CONFIDENTIAL | CONFIDENTIAL | CONFIDENTIAL | CONFIDENTIAL | CONFIDENTIAL | CONFIDENTIAL |

# Clinical evaluations (physical examination, eye examination and ECG)

Eye examination (fundoscopy/fundusphotography) and ECG findings will be summarised descriptively, including:

- summaries
- the change from baseline after 26 weeks of treatment

Any findings in the physical examination evaluation at screening will be presented as listings. Any clinically significant deterioration of a pre-existing condition after the screening visit, as well as any new clinically significant findings will be recorded as adverse events.

### Laboratory assessments

All laboratory parameters will be summarised descriptively.

The following tables will be presented based on both observed and LOCF imputed data:

- Shift tables from baseline to after 26 weeks of treatment
- Proportion of subjects with measurements outside reference range by treatment and week

Laboratory values will be presented graphically as box plots by treatment and week.

For each laboratory parameter, individual values outside the reference ranges (abnormal values) will be listed.

For lipase and amylase the following rule applies in the evaluation of the result

• If the amylase or lipase baseline (at screening) value is > 3xUNR the information will be recorded as medical history for that subject.

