Follow-up visit (FU)	SC	R	V	V	T	V	T	V	T	V	T	V	T	V	T	V	FU
Visit number															23		
							7		11		15		19		24 25		
							8		12		16		20		26		
	1	2	3	4	5	6	9	10	13	14	17	18	21	22	27	28	29
Time of visit (week)															21		
	-21		,	_	2		5 6		9	10	13	1.0	17	20	22	26	27
	-2	0	1	2	3	4	7	8	10 11	12	14 15	16	18 19	20	23 24	26	27
							_ ′		11		13		17		25		
Visit window (days)			±3	±3	±3	±3	±3	±3	±3	±3	±3	±3	±3	±3	±3	±3	+3
Hypoglycaemic episodes		X	X	X	X	X	X	X	X	X	X	X	X	X	X	X	X
ECG 	X															X	
Eye examination 5	X															X	
Physical examination	X															X	
Vital signs	X	X								X						X	
Antibodies		X								X						X	X
Biochemistry	X	X								X						X	
Haematology	X	X								X						X	
Hormones, calcitonin	X	X								X						X	
Lipids		X								X						X	
Urine dipstick		X								X						X	
Pregnancy test (blood sample)	X															X	
REMINDERS						•	•	•			•		•	•			
Handout ID card	X																
Handout and instruct in BG-meter use	X																
Attend visit fasting		X				X		Х		X		X		X		X	x 
IV/WRS call	X	X				X		X		X		X		X		X	Λ
Dispense trial product. Instruct																	<del>                                     </del>
and hand out Directions for Use.		X				X		X		X		X		X			
Drug accountability		X				X		X		X		X		X		X	
Handout and instruct in/collect diary	X	X	X	X		X		X		X		X		X		X	X
Collect first date and dose of trial			X														
Product  Collect last date and dose of trial		 	 	 	 				 							v	
product																X	
Confirmation of unchanged dose of metformin			X	X	X	X	X	X	X	X	X	X	X	X	X	X	
For liraglutide arm:																	
Confirmation of unchanged dose						X	X	X	X	X	X	X	X	X	X	X	
of liraglutide 																	
End of trial and sign off on case																	X
book	1	1	1	1	1	l	l	l	1	1	L		L	L			Щ

- 1. Screening must take place within 14 calendar days prior to randomisation.
- 2. For source data to be recorded in subject's diary prior to every PK sampling visit, please see section 8.3.4.
- 3. For IDeglira and IDeg arm: Daily pre-breakfast SMPG, last dose prior to titration and dose to be taken after titration must be recorded. For liraglutide arm: Pre-breakfast SMPG on 3 consecutive days prior to each visit/telephone contact must be recorded.

Protocol		Date:	07 October 2014	Novo Nordisk
Trial ID: NN9068-4148	CONFIDENTIAL	Version:	2.0	
UTN: U1111-1154-6671	CONFIDENTIAL	Status:	Final	
		Page:	14 of 84	

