### 5.6 Rationale for treatment

Enrolment of insulin-naïve subjects with T2DM, inadequately controlled on 1-2 OADs, has been chosen to demonstrate the efficacy and safety of IDegLira, when added to metformin.

The rationale for including subjects with pre-trial treatment metformin ± one other OAD is to mimic common practice of diabetes treatment in subjects with T2DM failing on 1-2 OADs and will prevent undue heterogeneity of the treatment arms due to diverse treatment. The daily dose of metformin (≥ 1500 mg or max tolerated dose) is close to the maximum recommended dose as per local labelling for the treatment of type 2 diabetes.

When glycaemic control is not achieved or sustained on this background, the addition of another OAD, or initiation of GLP-1 receptor agonists, basal insulin or IDegLira can be considered.

The expected outcome after 26 weeks of treatment with IDegLira compared to IDeg is similar change in HbA1c, less weight gain, lower post-prandial glucose levels, and a lower rate of hypoglycaemic events. In comparison with liraglutide a greater decrease in HbA1c, a lower FPG level and fewer gastro intestinal AEs are anticipated for IDegLira. For more detailed information on IDegLira, please see Investigator's Brochure or any updates hereof.

IDeg and liraglutide have been included as comparators in order to comply with regulatory requirements to assess the risk benefit profile of the combination product as compared to the individual components.

Apart from metformin, other OADs are primarily excluded at randomisation because they are not approved for use combined with liraglutide and metformin by the CFDA and are also not supported by the China clinical programme for liraglutide in terms of safety (and efficacy).

Metformin treatment will be in accordance with locally approved label.

Date: 07 October 2014 | Novo Nordisk Protocol Trial ID: NN9068-4148 Version: 2.0 CONFIDENTIAL UTN: U1111-1154-6671 Final Status: 22 of 84

Page:

#### **Trial population** 6

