### 8.1.8 Subject withdrawal

If a subject is withdrawn from the trial, the investigator must aim to undertake procedures similar to those described for Visits 28 and 29 as soon as possible. The end-of-trial form must be completed, and final drug accountability must be performed even if the subject is not able to come to the trial site. A withdrawal session must be made in the IV/WRS. The case book must be signed.

Although a subject is not obliged to give his/her reason(s) for withdrawing from a trial, the investigator must make a reasonable effort to ascertain the reason(s), while fully respecting the subject's rights. Where the reasons are obtained, the primary reason for not completing the trial must be specified on the end-of-trial form in the eCRF.

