# 17 Statistical considerations

Novo Nordisk will analyse and report data from all sites together.

All analyses of efficacy and safety endpoints will be based on the full analysis set (FAS). The analysis of the primary endpoint will be repeated on the per-protocol (PP) analysis set and the completer analysis set (CAS) for sensitivity purposes. All efficacy endpoints will be summarised using the FAS and safety endpoints will be summarised using the safety analysis set (SAS).

The impact of protocol deviations and outliers may be investigated further in sensitivity analyses if deemed relevant.

Unless otherwise specified, all continuous measurements will be summarised descriptively at each visit by treatment using observed data. After 26 weeks of treatment, descriptive statistics will be presented based both on observed and last observation carried forward (LOCF) imputed data. Endpoints that are analysed untransformed and endpoints that are not formally analysed are summarised by the arithmetic mean, standard deviation (SD), median, and minimum and maximum value. Endpoints that are analysed log-transformed are supplemented with the geometric mean and coefficient of variation (CV).

For measurements over time, mean values will be plotted to explore the trajectory over time. LOCF imputed data will be used as the basis for plotting data, if not otherwise specified. For endpoints that are analysed log-transformed, the geometric mean values will be plotted.

A standard analysis of covariance (ANCOVA) model will be applied for the continuous primary and secondary endpoints. The model includes treatment and previous OAD treatment (metformin or metformin in combination with one of the following: AGI, SU, glinides and TZD as fixed effects and the corresponding baseline value as covariate. In the following, this model will be referred to as the standard ANCOVA model.

Presentation of results from a statistical analysis will include the estimated mean treatment effects (Least Square Means [LSMeans]) for absolute values and change from baseline. In addition, estimated mean treatment difference (or ratio) will be presented together with the two-sided 95% confidence interval and corresponding two-sided 5% p-value.

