### Handling of missing data

The expected percentage of missing data is around 15%. In accordance with industry guidance endpoints will be assessed at frequent visits and also on subjects who withdraw prematurely. This will facilitate an analysis in accordance with ITT principles. Also, the combined information on frequent outcomes and information on reason for drop-out is assumed to account for the missing data anticipated.

Protocol Trial ID: NN9068-4148 UTN: U1111-1154-6671	CONFIDENTIAL	Date: Version: Status: Page:	07 October 2014 2.0 Final 60 of 84	Novo Nordisk
---	--------------	---------------------------------------	---	--------------

If an assessment has been made both at screening (Visit 1) and randomisation (Visit 2), and if not otherwise specified, the value from the randomisation visit will be used as the baseline value. If the value measured at the randomisation visit is missing and the assessment also has been made at screening, then the screening value will be used as the baseline value.

Missing values (including intermittent missing values) will be imputed using the LOCF method. Subjects without data after randomisation will be included by carrying forward their baseline value. LOCF has been a standard approach in diabetes trials for many years, and was used as the primary analysis in both IDegLira and IDeg phase 3a trials. LOCF is considered to be an appropriate method in the context of TTT trials, where subjects after withdrawal typically continue their therapy using commercially available insulin. In previous TTT trials with IDegLira and IDeg, LOCF has generally provided similar results to alternative methods applied to handle missing data, such as repeated measures models and completer analyses. In this trial, similar sensitivity analyses will be made to examine the robustness of the LOCF method. The LOCF approach will also be used to impute missing values in CAS.

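### The LOCF version of the laboratory shift and out-of-range tables lets a pre-treatment baseline value stand in for a missing week-12 or week-26 result

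*Protocol*

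**What the plan says.** Section 17.4.2.2, Laboratory assessments, specifies two tables: shifts from baseline to week 26, and the proportion outside the reference range by treatment and week. It adds: "The following tables will be presented based on both observed and LOCF imputed data". It also asks for box plots by treatment and week and a listing of every individual value outside the reference range.

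The LOCF rule itself is in section 17, Handling of missing data: "Missing values (including intermittent missing values) will be imputed using the LOCF method", and "Subjects without data after randomisation will be included by carrying forward their baseline value". When an assessment was made at both screening and Visit 2, "the value from the randomisation visit will be used as the baseline value"; if that value is missing, the screening value is used. Either way, baseline precedes treatment. The laboratory paragraph has no rule of its own.

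Three other places matter:

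- Safety endpoints are summarised on the safety analysis set, which needs one dose and no post-baseline sample (sections 17 and 17.2).
- The flow chart (section 2) schedules on-treatment biochemistry and haematology at weeks 12 and 26 only.
- On withdrawal, "the investigator must aim to undertake procedures similar to those described for Visits 28 and 29 as soon as possible" (section 8.1.8). Visit 28 includes biochemistry and haematology.

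**The concern.** A shift table is read as the share of exposed subjects whose result moved on treatment. A subject with only a pre-treatment result carries no information on that. Under the general rule the subject is nevertheless placed at week 26 with the baseline value, falls on the diagonal by construction, and stays in the denominator. In the by-week table, the week-12 column can also hold a baseline value for a subject who merely missed the week-12 sample and later completed.

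The protocol's reason for LOCF does not reach these data. It argues that subjects leaving a treat-to-target trial usually continue on commercially available insulin. That bears on glycaemic endpoints, not on liver or pancreatic enzymes or creatinine, and the liraglutide arm is not titrated to target.

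At stake is a small understatement of laboratory shifts in a descriptive safety table. It could differ between arms if the share of unsampled subjects differs.

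**Working it through.** **Inputs.** From the protocol: 720 randomised 2:1:1, hence 360, 180 and 180 (sections 5.1 and 6.1); anticipated withdrawal 15%, not split by arm (section 6.1). Not in the protocol: the true shift rate p, and the share f of dosed subjects with no post-baseline sample. Both are assumed below. The protocol states no figure for laboratory shifts, so there is none to reproduce.

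**Step 1: size of the dilution.** Of N dosed subjects, N(1 - f) have a post-baseline value and p × N(1 - f) of them shift. The remaining fN are entered as no shift. The LOCF table shows

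p × N(1 - f) / N = p(1 - f).

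| True rate p (assumed) | f = 2% | f = 5% | f = 10% | f = 15% |
|---|---|---|---|---|
| 5% | 4.9% | 4.75% | 4.5% | 4.25% |
| 10% | 9.8% | 9.5% | 9.0% | 8.5% |
| 20% | 19.6% | 19.0% | 18.0% | 17.0% |

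The 15% column requires every withdrawn subject to leave without any post-baseline sample. In an arm of 180 that is 27 unsampled and 153 sampled. At p = 10%, 15.3 subjects shift on average: 15.3/180 = 8.5% in the LOCF table, against 15.3/153 = 10% among those sampled.

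**Step 2: arms with unequal f.** With the same true rate of 10% and assumed shares of 5% and 15%, the table shows 9.5% and 8.5%. This is a spurious gap of 1.0 point (ratio 0.85/0.95 = 0.895). At p = 5% the gap is 0.5 points and at p = 20% it is 2.0 points.

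**Step 3: whether LOCF always lowers the count.** It does not. Assume 15% withdraw, 80% of them give a withdrawal sample, and the shift rate is 20% in withdrawn subjects and 10% in completers.

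- LOCF as planned: 0.85 × 0.10 + 0.15 × 0.80 × 0.20 = 0.085 + 0.024 = 10.9%.
- Observed week-26 table, completers only: 10.0%.
- All subjects: 0.85 × 0.10 + 0.15 × 0.20 = 11.5%.
- LOCF restricted to post-baseline values: 10.9% / (0.85 + 0.12) = 11.2%.

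Carrying a withdrawal sample forward is useful. Only the carried baseline does harm.

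**Step 4: out-of-range proportions.** The factor (1 - f) does not apply here. A subject in range at baseline is kept in range, and one out of range at baseline is kept out of range. For a parameter that improves on treatment, carrying baseline forward raises the proportion.

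**The case against.** The strongest reply is that the plan does not rest on the LOCF tables. The same sentence requires observed versions, and these carry no baseline forward. A week-12 abnormality that later normalises is counted in the observed by-week proportions. Every abnormal value is listed, and a clinically significant abnormality is an adverse event (section 12.1). The calcitonin categories are defined on post-baseline measurements. Withdrawal sampling should leave few subjects with nothing after baseline, and as step 3 shows, LOCF can then report more shifts than a completers-only table. All of this stands, and it limits the point to one version of two descriptive tables.

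It may also be said that the baseline rule was written with efficacy in mind. The text does not say so: the rule is general, and the laboratory paragraph invokes LOCF without redefining it. Nor is this a detail simply left to the SAP, because the rule as stated produces the wrong count. By contrast, whether to show worst on-treatment values may fairly be left there.

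A reader might infer that the LOCF tables will make liraglutide look safer, since "fewer gastro intestinal AEs are anticipated for IDegLira". The documents do not support that. The statement concerns adverse events, not withdrawals, and still less withdrawals without a sample. No withdrawal or sampling rate is given by arm. A reader might also infer that the plan has no view of abnormalities arising at any time on treatment. The by-week tables, the listing and the calcitonin categories show otherwise.

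**Conclusion.** The point holds in a narrow form. In the LOCF version of the laboratory shift table, dosed subjects without a post-baseline sample are counted as no shift, and the shift proportion is understated by the relative amount f. If withdrawal runs as anticipated and completers are sampled, f is at most 15% overall, where an assumed 10% rate shows as 8.5%. With withdrawal sampling working, f would be smaller. The 15% is not a bound for any single arm, because it is not split by arm. A between-arm distortion is therefore possible but of unknown size and direction. The factor also treats sampled and unsampled subjects as having the same shift rate. For the out-of-range table, a baseline value can replace an on-treatment one, but the direction of the error is not fixed. The observed tables, the calcitonin categories, sample size, power and all confirmatory tests are unaffected. This is a minor correction to descriptive safety output.

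**What to change.** In section 17.4.2.2, Laboratory assessments:

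- State that the LOCF tables carry forward only post-baseline values, including the withdrawal sample, and never baseline.
- Use as denominator the subjects in the safety analysis set with at least one post-baseline value (in the by-week table, one by the week shown).
- Show the number without such a value as missing, by arm.
- Keep the observed tables as they are.
- Optionally, add a shift table from baseline to the worst post-baseline value.

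This follows the post-baseline logic that the same section already uses for the calcitonin categories and the urinalysis listing. The cost is table programming; no data collection, sample size or test changes. The small downside is that denominators fall slightly below the number exposed and must be displayed.
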